2. STUDY DESIGN

2.1 Study summary and flow diagram

This is a mixed-methods, study to establish the clinical criteria to indicate that continuing resuscitation is futile; when the decision to discontinue resuscitation should be made; who should make the decision and where the decision should be made, among adult out of hospital cardiac arrest patients who do not respond to resuscitation efforts.

This section presents an overview of the study, its ethical considerations and procedures across the five work packages (WPs). Details of the individual WPs are following in sections 3 (WP1), 4 (WP2), 5 (WP3), 6 (WP4) and 7 (WP5).

The study consists of five WP's with the following objectives:

Figure 1: PROTECTeD Project Summary

Objectives:

- Summarise evidence concerning predictors of survival, non-survival, and termination of resuscitation (TOR) rules (WP1)
- Survey English ambulance services regarding TOR practices (WP2)
- Examine OHCAO data assess adherence to ROLE and to model alternate TOR rules (WP3)
- Interview paramedics, ED clinicians and survivors/relatives to better understand issues relating to TOR (WP4)
- Synthesize findings, present at national consensus meeting and draft new TOR guidance for paramedics (WP5)

WP1 Systematic Review

- Identify predictors of survival
- Identify predictors of non-survival
- Identify TOR rules
- Summarise performance of TOR rules

Set up • Ethics • Governance • Set up processes		 Review am Identify and Identify loc 	y English ambulance servi abulance service documenta eas of consistency & variatio cal modifications to ROLE preeived risks	tion on •	WP5 Consensus Conference Present evidence from previous work packages Use a Nominal Group Technique (NGT) to identify issues relating to TOR
		 Determin Identify i Establish resuscita Model ef 	Examine OHCAO database the if ROLE is followed inconsistent practice the mean/median duration tion in cases of ROLE fects of alternative TOR ru t rates & survival	e · · · · · · · · · · · · · · · · · · ·	Prioritise the issues raised during the NGT Identify consensus solutions to the prioritised issues Draft an updated TOR rule for use by paramedics Report writing & dissemination of findings
	 WP4 Interviews with clinicians and survivors/relatives Understand the experiences relating to out of hospital TOR Identify barriers and facilitators to out of hospital TOR Identify ethical issues concerning out of hospital TOR 				
0 Timeline (months)	6	12	18	24	30 36

2.2 Aims and objectives

2.2.1 Primary objective

To develop an evidence based guideline that assists paramedics, when making decisions during out of hospital cardiac arrest that optimises outcomes for patients and is sensitive to needs of relatives and demands on NHS services.

2.2.2 Secondary objective

Study flow diagram is shown in figure 1:

- WP 1: Describes the content and performance characteristics of existing termination of resuscitation rules in adults who are treated for out of hospital cardiac arrest.
- WP 2: Identifies areas of consistency, variation and clinical risk associated with termination of resuscitation practices across the UK ambulance services.
- WP 3: Examines current NHS ambulance termination of resuscitation practice and model effects of alternative rules on patient flow and outcomes.
- WP 4: Explores the perspectives of patients, relatives, paramedics and emergency medicine staff and consider the ethical aspects of termination of resuscitation rules.
- WP 5: Synthesises the information obtained above to develop evidence based, ethically grounded, consensus guidelines, that optimise outcomes for patients and are sensitive to the needs of relatives and the demands on NHS services.

2.3 Recruitment Summary

Work packages 1, 2, 3 and 5 will not be recruiting participants.

Work package 4:

Recruitment within WP4 will continue until we have interviews with a maximum of 30 ambulance staff and 30 ED staff, continuing until data saturation. We expect to recruit approximately 15 patient/family members for interviews who had direct experience of the cardiac arrest (for family members this means they were present at the time of the arrest and treatment by the ambulance crew/hospital staff). Interviews may also include family members who express interest in the study but were not present at the event. We expect up to 5 of these interviews. The number of cardiac arrest events may be more than 20 as not all stakeholders will be involved in any one event. The maximum number of cardiac arrest events will be 75.

2.4 Eligibility criteria

Participants are eligible to be included in the study (WP4) if they fall in the categories outlined in 2.3 above.

2.4.1 Exclusion criteria

- 1. Lack of provision of informed consent (written or verbal)
- 2. Aged under 18

3. Known to be a prisoner

3. SYSTEMATIC REVIEW (WP1)

Aim: To describe the characteristics and performance of termination of resuscitation rules in adults who are treated for out of hospital cardiac arrest.

Objectives:

- Identify the content and structure of existing termination of resuscitation rules
- Summarise performance characteristics of termination of resuscitation rules

Plan of Investigation: The protocol for the systematic review will be registered with the International Prospective Register of Systematic Reviews (CRD42019131010). It will be conducted in accordance with recommendations from the Cochrane Screening and Diagnostic Tests Methods Group and reported in accordance with the Preferred Reporting Items for a Systematic Review and Meta-analysis of Diagnostic Test Accuracy Studies: The PRISMA-DTA Statement.⁵⁶

Search Strategy: Systematic searches of MEDLINE, EMBASE, CINAHL, EconLit, Web of Science and the Cochrane Database will be performed. Search strategies, combining MeSH terms and Key Word searching, will be developed in collaboration with a medical information specialist. Quality assurance strategies will include ensuring key papers are retrieved, reviewing the reference lists of included papers and contacting subject experts.

Study Selection: Studies will be included based upon a-priori defined inclusion/exclusion criteria. Two reviewers will independently evaluate each study identified against the inclusion/exclusion criteria. Where reviewers disagree, a third reviewer will adjudicate. Kappa statistics will be reported for reviewer agreement.

Inclusion Criteria:

- Language: No language restrictions will be placed. It is expected that a small proportion of non-English citations will be identified. Where such studies are identified, we will contact the author to ask if an English translations is available. If no English translation is available from the author we will attempt to obtain a translation by informal methods. Where informal methods fail, we will exclude the study. Google translate (or similar engine) will not be used to translate non-English citations. A record of non-English citations will be maintained to gauge how much potential evidence has been excluded from the systematic review.
- Publication type: original research published in peer reviewed journals.
- Study Design: systematic reviews, meta-analyses, randomised controlled trials, case-control studies, cohort studies, cross-sectional studies, retrospective analyses, economic evaluations, modelling studies.
- Study Population: adult patients suffering out-of-hospital cardiac arrest.
- Intervention/s: termination of resuscitation rules.
- Comparators: alternative rules, usual care and/or standard practice.
- Outcomes: performance characteristics of identified termination of resuscitation rules.

- Setting: out-of-hospital.
- Timing: all-cause mortality up to 30 days or hospital discharge.

Exclusion Criteria:

- Publication type: narrative reviews, letters, editorials, commentaries, books and book chapters, lectures and addresses and consensus statements.
- Study Design: case reports and/or studies that fail to report their methods.
- Study Population: in-hospital studies and/or animal studies.

The systematic review process will consist of data being extracted independently by one reviewer using standardised definitions. Data extracted will be documented and independently checked for accuracy by a second reviewer. Uncertainties will be resolved by discussion. Those that cannot be resolved will be referred to the rest of the project team. Where multiple publications of the same study are identified, data will be extracted and reported as a single study.

The methodological quality of each included study will be assessed by one reviewer and checked by a second. A critical appraisal tool appropriate to study design will be utilised to assess the quality of each included study. Risk of bias will be assessed using the ROB-2 instrument for randomised controlled trials⁵⁷ and ROBINS-I instruction for non-randomised trials⁵⁸ as per recommendations of the MRC Network Hubs for Trials Methodology Research. An adapted QUADAS-2⁵⁹ will be used to assess studies of diagnostic accuracy and PROBAST⁶⁰ will be used to assess prediction modelling studies. The CHEERS checklist⁶¹ will be used to assess the quality of economic evaluations. Quality of evidence will be reported as per GRADE working group recommendations.⁶²

considered to give pooled sensitivity and specificity estimates, stratified by triage tool. Study specific estimates of sensitivity and specificity will initially be compared in coupled Forest plots and if relevant summary receiver operating curves.^{64,65} Variability will be assessed systematically. In the absence of variability, a hierarchical random effects bivariate model will be used for binary index tests to calculate summary values for sensitivity and specificity, with associated 95% confidence intervals.^{64,65} The results of the economic evaluations will be reported in the form of a narrative synthesis. Informed by the retrieved studies the following post hoc analyses may be performed: investigating heterogeneity (meta-regression models); comparing the performance of different triage tools (a multilevel bivariate model or the Rutter and Gatsonis HSROC method) and sensitivity analyses examining the effect of methodological quality and differing study population or settings.^{64,65} Reporting biases will be evaluated using Deek's method of examining effective sample size funnel plots with associated regression test of asymmetry used to detect publication bias and other sample size related effects.⁶⁶ However, the limitations of methods to detect publication bias in diagnostic accuracy data are acknowledged.

Output: We will publish a manuscript with clear description of the study background, methods and results, presented in accordance with Preferred Reporting Items for a Systematic Review and Metaanalysis of Diagnostic Test Accuracy Studies.⁵⁶ It will summarise the performance characteristics (sensitivity, specificity, negative and positive predictive values) for termination of resuscitation rules among adults who sustain an out of hospital cardiac arrest and their influence on transport rates. The overall strength of supporting evidence will be reported in accordance with GRADE system.⁶²

Insufficient evidence will be highlighted if conclusions cannot be drawn because there are too few reliable studies, or too much uncertainty.

4. NATIONAL REVIEW OF TERMINATION OF RESUSCITATION PRACTICES (WP2)

4.1 Study design for WP2

Aim: Identify areas of consistency, variation and clinical risk associated with termination of resuscitation practices across UK ambulance services.

Objectives:

- Review the policies, procedures, clinical notices and education packages relating to termination of resuscitation in each ambulance service
- Identify areas of consistency and variation, in resuscitation practices between ambulance services
- Identify local modifications to the ROLE guideline by each ambulance service
- Determine how policies and procedures for termination of resuscitation are implemented in each ambulance service
- Understand the organisational risks associated with providing resuscitation services, as perceived by senior personnel in each ambulance service

Plan of investigation: We will ask each ambulance service to provide copies of all documents (policies, procedures, clinical notices, operational notices, briefings, training notices and any education and

training materials) relating to termination of resuscitation by ambulance staff within their trust. We will then undertake a document analysis to examine consistency and variation in termination of resuscitation practices between ambulance services. We will specifically look for evidence of local modifications to the national ROLE guidance. We will further explore the timing, structure and content of relevant education packages relating to termination of resuscitation.

Finally, we will present our findings to a meeting of the National Leads Group and invite their feedback to identify those areas of clinical practice relating to cardiac arrest decision making that they believe are most challenging for ambulance services and to explore perceived organisational risks and concerns associated with the current ROLE guidelines.

4.2 Data management for WP2

Any documents supplied by ambulance service collaborators will be managed in accordance with WCTU policies and procedures. Contemporaneous notes taken during meeting where our findings are presented to the National Leads Group will be stored in accordance with WCTU policies and procedures. No audio recordings will be made.

4.3 Data analysis for WP2

Findings will be collated and tabulated to present a national overview of current policies, training and implementation of termination of resuscitation.

4.4 Output for WP2

Output: Understanding of consistency and variation in resuscitation practices and clinical risk concerns among ambulance services.

5. ANALYSIS USING OHCAO REGISTRY DATA (WP3)

5.1 Study design for WP3

Aim: Examine current NHS ambulance termination of resuscitation practice and model effects and cost effectiveness of alternative rules on patient flow and outcomes

Objectives:

- Analyse the Out-of-Hospital Cardiac Arrest Outcomes (OHCAO) registry data to describe current practice across ambulance services in England and Wales.
- Model the effects and cost-effectiveness of alternative termination of resuscitation rules on both transport rates and survival to hospital discharge.

Plan of investigation: we will use the OHCAO registry which collects information from all English and the Welsh Ambulance Services on patients who are treated by ambulance personnel for an out of hospital cardiac arrest. The registry, hosted by the University of Warwick, is structured and maintained in accordance with the Utstein Guidelines for resuscitation registries,⁶⁷ and details of it have been summarised previously.⁶⁸ The National Research Ethics Service granted ethics approval, reference number 13/SC/036. The Confidential Advisory Group (CAG), reference number ECC8-

04C/2013, granted approval to use identifiable patient information where it is not practical to obtain consent.

Sample size: Using the registry data and taking the lowest prevalence (most conservative) of 18%, from the three outcomes (recognised of life extinct, ROSC at hospital handover and CPR transported to hospital), a sample of 94, 000 patients would be required to detect 0.0015 precision in maximum clinically acceptable width of the 95% confidence interval of both the sensitivity (true positives) and specificity (true negatives). This sample size would also allow a test sensitivity of 99% to be detected using 5% as the type I error rate. We anticipate that the number of cases in the registry (during 2014-2018) will be approximately 132,000 and therefore our sample will provide very accurate estimates of sensitivity and specificity, in relation to the population

Withdrawals and exclusions: WP3 is using routinely collected anonymised data from the OHCAO registry. Any concerns patients had about their anonymised information being included, should have been addressed by the organisation collecting the data at the time. Withdrawal will not be possible from the anonymised data provided to the study team.

5.2 Data collection for WP3

Data collection: The OHCAO registry collects data on individual patient demographic, cardiac arrest event characteristics, ambulance response times, treatments administered, response to treatment, whether the patient was transported to hospital with or without ongoing CPR, whether and when return of spontaneous circulation was achieved and the final outcome (survival to hospital discharge). The database currently has information from over 150,000 cases of out of hospital cardiac arrest.

5.3 Data management for WP3

Data management: Data will be sent securely from the OHCAO Registry in an anonymised format, in accordance with Warwick SOPs. Data sharing will follow OHCAO processes. No formal data sharing agreement is required due to the University of Warwick being the legal entity for both the OHCAO Registry and PROTECTED project.

5.4 Data analysis for WP3

Data quality checks: data quality checks are performed within the OHCAO study according to the OHCAO protocol, which includes data being validated by the OHCAO web application upon submission from the AS and annual data cleaning, prior to the transfer of the clean anonymised data set to PROTECTED study for analysis.

Data analysis: We will use descriptive statistics to summarise current practice by reporting patient characteristics (age, gender), cardiac arrest characteristics (cause, initial rhythm, witness status, bystander CPR), hospital transfer rates and survival status according to whether (a) resuscitation was terminated on scene, (b) return of spontaneous circulation was achieved or (c) the patient was transported to hospital with on-going CPR. We will estimate costs based on data from the PARAMEDIC2 trial.⁶⁹ Results will be presented individually for each of the English and Welsh Ambulance Services. We will calculate the proportion of patients who fulfilled the national ROLE criteria for each ambulance service and whether resuscitation was terminated at scene or the patient was transported to hospital to highlight any discordance between policy and practice. We will describe the number and characteristics of patients where resuscitation was discontinued at the scene but they did not fulfil the

termination of resuscitation criteria. We will also report exceptions where the termination of resuscitation criteria indicated resuscitation would be unsuccessful but the patient survived.

We will model the impact of alternative termination of resuscitation rules identified in WP1 and report the impact of their use on the proportion of patients in whom resuscitation would be discontinued at the scene versus transport in to hospital. We will examine the performance of the different rules by calculating the sensitivity, specificity, positive predictive value, negative predictive value and their 95% confidence intervals for each of the alternative TOR rules. We will use the current JRCALC ROLE guideline as the gold standard. In order to determine the significance of the difference in sensitivity and specificity of each of the alternative TOR rules, statistical evaluation will be performed using appropriate tests, e.g. McNemar test with Yates Correction. We will compare model performance by performing a ROC analysis and analyse differences in test performance using De Long's method for comparing c-statistics.

We are aware that our approach will be confounded by the self-fulfilling prophecy bias outlined above. However, the intention of this work package is to compare alternative rules to current national guidelines. These risks are therefore less relevant than if we claimed to be under taking an independent evaluation of alternative rules.

We will additionally develop a decision-analytic model that will estimate the cost-effectiveness of the current JRCALC ROLE guideline and alternative termination of resuscitation rules. The model will be informed by data extracted from the OHCAO registry data as well as data identified in the published literature, including data identified in WP 1. Cost-effectiveness will be expressed in terms of incremental cost per additional survivor to hospital discharge. Multi-parameter uncertainty in the model will be addressed using probabilistic sensitivity analysis, and the probability of cost-effectiveness of each strategy shown in cost-effectiveness acceptability curves.

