1. BACKGROUND

1.1 Epidemiology and burden of the condition

NHS Ambulance services respond to approximately 60,000 out of hospital cardiac arrest events each year. In approximately half of these cases the patient is obviously deceased on arrival of the ambulance crew, and resuscitation is not attempted.¹ However, whenever there is a chance of survival, no matter how slim, ambulance crews will always attempt resuscitation.² Unfortunately, the majority of resuscitation attempts are unsuccessful. Paramedics cease resuscitation efforts in the field in approximately 10,000 cases, and transport the remaining 20,000 patients to hospital (14,000 with CPR in progress and 6,000 after return of spontaneous circulation (ROSC)). Among all the patients where resuscitation is attempted, only 7-8% will survive to hospital discharge.¹

The decision to cease resuscitation or transfer to hospital is informed by the national Recognition of Life Extinct (ROLE) guideline.² A key purpose of the ROLE guideline is to distinguish between those patients who have no chance of survival, where resuscitation efforts can be safely discontinued without transfer to hospital, and those patients with any chance of survival, no matter how slim, where transport to hospital, to avail the patient of the additional resources and expertise, is indicated. The ROLE criteria were implemented over 20 years ago based on expert opinion and anecdotal clinical experience.

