1.2 Existing knowledge

A number of different approaches exist to determine when on-going resuscitation efforts have negligible chance of success. These can be broadly classified as (i) time based considerations , (ii) those based on the clinical characteristics of the patient and their response to treatment and (iii) those which use ancillary tests. The benefits of transfer with on-going CPR are uncertain with some evidence suggesting it may be harmful. There is a paucity of evidence concerning what impact discontinuing resuscitation at the scene has on relatives and care providers.

Time based decisions

The Recognition of Life Extinct (ROLE) guideline (based on the European Resuscitation Council termination of resuscitation rule)² combines cardiac arrest event characteristics (asystole) with a failure to respond to treatment within 20 minutes of the initiation of advanced life support. Under this guideline patients who continue to have evidence of electrical activity on the ECG (including agonal heart rhythm, slow pulseless electrical activity) are recommended for transport to hospital.

There have been no published evaluations of the performance of the ROLE guideline in the UK. The ROLE guideline was retrospectively applied to a cohort of patients enrolled in the Swedish Cardiac Arrest Registry (1990-2007). The rule was 95% sensitive (95% CI: 91.3–97.5) and 99.9% specific (95% CI: 99.9–99.9) for identifying cases where on-going resuscitation efforts were not associated with long term survival .³ In order to correctly validate termination of resuscitation rules, all patients to whom the rule is applied must be transported regardless of the decision the rule indicates. This and many other retrospective studies of this nature are limited as protocols in place at the time already allowed termination of resuscitation (in this study after 30 minutes). This runs the risk of a phenomenon referred to as self-fulfilling prophecy bias – knowledge of the test result leads to termination of resuscitation. This trial was also limited by the inclusion of data that are over 25 years old. Resuscitation practice and outcomes have improved since the study was published which may limit generalisability to current day practice.^{1,4}

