We may be allowing as many as 300 people a year to die unnecessarily from terminating resuscitation too early.⁵³ By contrast, the un-selective transfer of 20,000 patients per year with ongoing CPR is

resource intensive at times of growing pressure on emergency services and places ambulance staff and others at risk of death or serious injury.³⁶

Expressed need

This proposal is highly relevant to the needs of patients and the NHS. This need is articulated through:

- (i) National policy documents that place a high priority on improving survival from cardiac arrest
- (ii) A desire to deliver the right care to the right patient at the right time
- (iii) The drive to reduce variation in the NHS as a whole and specifically within ambulance services
- (iv) The government's commitment to improve end of life care
- (v) The need to optimise emergency care pathways to reduce ED overcrowding and deliver better care
- (vi) NHS Ambulance Cardiac Leads Group prioritising this subject as one of the most important areas for further research.

Sustained interest and intent

As the number of cardiac arrests increases year on year and demand on acute services continues to grow, the results of this research will remain highly relevant and important to the needs of the NHS in the future.

New knowledge

Health systems from which existing data are derived differ from the UK setting (e.g. the US use a two tier ambulance response system, in Asia, paramedics are not allowed to terminate resuscitation). Very little information is known about patient and relatives experience. This creates the specific need to generate new knowledge that is embedded in and generalisable to the NHS.

Generalisability and prospects for change

This work will draw on NHS data to quantify and model the effect of new approaches to resuscitation decision making on patient flow and outcomes. It will seek the views of front line NHS clinicians from the ambulance and hospital setting and senior staff within ambulance services. It will explore, for the first time, the perspectives of relatives of victims of cardiac arrest, treated by the NHS. It will develop new treatment pathways in partnership between patient and public representatives and ambulance services.

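### WP3 discounts self-fulfilling-prophecy bias because it compares rules with ROLE, but ROLE informed the terminations behind the outcomes, so the bias is differential and favours ROLE to the extent that crews followed it

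*Protocol*

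**What the plan says.** Protocol section 1.2 explains the bias: "knowledge of the test result leads to termination of resuscitation". It also sets the condition for a valid validation, that "all patients to whom the rule is applied must be transported regardless of the decision the rule indicates". On this ground it faults a retrospective application of the ROLE guideline to a Swedish registry.

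Section 5.4 concedes the problem for WP3: "We are aware that our approach will be confounded by the self-fulfilling prophecy bias outlined above". It then argues that "the intention of this work package is to compare alternative rules to current national guidelines", and concludes: "These risks are therefore less relevant than if we claimed to be under taking an independent evaluation of alternative rules".

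Three other statements bear on that conclusion:
- Section 1.1: "The decision to cease resuscitation or transfer to hospital is informed by the national Recognition of Life Extinct (ROLE) guideline".
- Section 1.1, out of about 30,000 resuscitation attempts a year: "Paramedics cease resuscitation efforts in the field in approximately 10,000 cases".
- Section 1.4, as part of the case for the study: "We may be allowing as many as 300 people a year to die unnecessarily from terminating resuscitation too early".

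Section 5.4 plans sensitivity, specificity and predictive values for each alternative rule, tests of the differences, and a decision model giving cost per additional survivor to discharge. It names no analysis that addresses the bias.

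**The concern.** Comparing rules in the same data removes a bias only if the bias acts equally on the rules compared. Here it does not, because one of them helped to produce the outcomes.

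- A patient who would have survived but was stopped under ROLE is recorded as dead. ROLE is credited with a correct call. A rule that would have continued is charged with failing to identify a death.
- A patient who met an alternative rule but not ROLE, and was continued, has a visible outcome. If that patient survived, the alternative is charged with a false positive.

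Patients stopped at scene have a recorded survival of zero. They are about one third of attempts (10,000 of 30,000). Within that group, registry data alone cannot show a single survivor gained by a rule that would have continued. Yet possible loss of survivors through early stopping is one of the study's stated reasons. The results feed the decision model and, through WP5, a guideline expected to replace ROLE.

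**Working it through.** **The plan's own WP3 figure.** Section 5.1 asks for 94,000 patients. With sensitivity 0.99, 0.0015 read as the half-width and prevalence 0.18: 1.96² × 0.99 × 0.01 / 0.0015² / 0.18 = 93,906. The figure reproduces and is not in dispute. It shows that sampling error is meant to be about 0.15 percentage points, a yardstick for the bias.

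**Inputs.**
- Attempts 30,000 and scene terminations 10,000 a year (section 1.1).
- Survival to discharge 7–8% (section 1.1): 2,100 to 2,400 a year; midpoint O = 0.075 × 30,000 = 2,250.
- Hidden would-be survivors h: 0 to 300 a year. The top is the section 1.4 figure, used as an upper bound; 300/10,000 = 3% of scene terminations.
- Death is the positive outcome (section 3, stated for WP1), so specificity is the share of survivors whom a rule would not have stopped.

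**Step 1: ROLE alone.** Assume every hidden survivor was ROLE-positive and ROLE has no other false positives. Observed specificity is 100%; true specificity is O/(O + h).
- h = 0: 100%.
- h = 50: 2,250/2,300 = 97.8%.
- h = 300: 2,250/2,550 = 88.2% (87.5% with O = 2,100; 88.9% with O = 2,400).

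**Step 2: does the comparison cancel it?** Suppose all terminations followed ROLE and all ROLE-positive patients were stopped. Let a be observed survivors flagged by alternative A but not by ROLE, and b hidden survivors flagged by ROLE but not by A.
- Observed specificity difference (ROLE minus A) = a/O.
- True difference = (a − b)/(O + h).

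The true numerator is no larger and the denominator no smaller, so the observed difference is never below the true one. Specificity is biased towards ROLE or is neutral.

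Illustration with assumed a = 20, h = 300, b = 200:
- Observed: ROLE 100.0%, A 2,230/2,250 = 99.1%; difference +0.9 points.
- True: ROLE 88.2%, A 2,430/2,550 = 95.3%; difference −7.1 points. The ranking reverses.

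If A spares two thirds of hidden survivors at any h, the ranking changes when 2,250 = 2,230 + (2/3)h, so at h = 30, or 0.3% of scene terminations.

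**Step 3: terminations outside ROLE.** Let a share f of the 300 have been stopped although ROLE was not met, and let A flag all of them; A still spares two thirds of the rest. True ROLE specificity is (2,250 + 300f)/2,550; true A specificity is (2,230 + 200(1 − f))/2,550. The observed difference stays at +0.89 points.

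| f | True ROLE | True A | True difference | Bias towards ROLE |
|---|---|---|---|---|
| 0 | 88.24% | 95.29% | −7.06 | +7.95 |
| 0.2 | 90.59% | 93.73% | −3.14 | +4.03 |
| 0.4 | 92.94% | 92.16% | +0.78 | +0.11 |
| 0.5 | 94.12% | 91.37% | +2.75 | −1.86 |

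The direction depends on how closely terminations tracked ROLE.

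**Step 4: sensitivity.** Even with full compliance the sensitivity difference can move slightly against ROLE. Assume 27,450 true deaths, of which 5,700 are flagged by ROLE only and 2,000 by A only, with all 300 hidden survivors flagged by both. The true difference is 3,700/27,450 = 13.48 points; the observed one is 3,700/27,750 = 13.33.

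**The case against.** The plan does not hide the bias. It explains it in section 1.2, admits it in section 5.4 and only gives it less weight. Several stronger readings are tempting, and the documents do not support them.

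- **That the bias always favours ROLE.** This needs terminations to have followed ROLE. Section 1.4 reports local modification of practice, and section 5.4 plans to describe patients stopped at scene who did not meet the criteria. Steps 3 and 4 show that the direction can change.
- **That ROLE's false positives are wholly invisible.** Section 5.4 will tabulate whether ROLE-positive patients were stopped or transported, and will report survivors in whom the criteria indicated futility. ROLE-positive survivors who were not stopped will be seen.
- **That 88% is a ceiling on ROLE's specificity.** It assumes that all hidden survivors were ROLE-positive; with 40% stopped outside ROLE the figure is 92.9%. The number hidden may also be zero. The 1.3% survival in the West Midlands pilot (3/227) is no substitute, since those patients were transported with ongoing CPR and none of the 89 who met the Morrison criteria survived.
- **That the decision model cannot reflect lost survivors.** It may also draw on published literature, and a probabilistic sensitivity analysis is planned.

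Two further objections carry weight. Section 5.4 names ROLE as the gold standard. Read literally, sensitivity and specificity would then measure agreement with ROLE, and survival would not enter. That is a separate problem; the bias would remain in modelled survival and cost per survivor. Also, sensitivity analyses are commonly left to a SAP, which is not shown. That does not answer the point: the protocol itself states a reason for discounting the bias, and the reason is wrong.

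**Conclusion.** The concern stands in a bounded form. The justification in section 5.4 is incorrect and sits badly with the condition in section 1.2. Comparison with the rule that informed termination makes the bias differential, and it is expected to favour ROLE to the extent that field terminations followed ROLE.

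On the protocol's own figures, the effect on ROLE's apparent specificity runs from nothing to about 12 points (100% down to 88.2%), against an intended sampling precision of 0.15 points. The upper end rests on three assumptions: 300 hidden survivors a year, all of them ROLE-positive, and no other ROLE false positives. The effect is smaller if some were stopped outside the criteria. The cell counts for the alternative rule are illustrative, because the documents give none. They show that a ranking can reverse, not that it will. Uncertainty about direction is a reason to analyse the bias rather than to give it less weight.

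**What to change.** 1. Delete the sentence in section 5.4 that discounts the bias. State instead that the outcome of scene-terminated patients under continued treatment is unobserved.
2. In the survival-based comparison of rules, vary the assumed survival of these patients from 0 up to the 3% implied by sections 1.1 and 1.4. Do so separately for ROLE-positive and off-criteria terminations, and report the value at which the ranking of rules changes.
3. Enter this probability as an uncertain parameter in the probabilistic sensitivity analysis already planned for the decision model.
4. Show an analysis limited to patients not stopped at scene only as a supplementary result, and state that it selects on ROLE's own action. With full compliance it would contain no ROLE-positive patients, so it cannot stand alone.

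Cost: a protocol or SAP paragraph and extra analysis runs, with no new data. Some accuracy and cost-effectiveness figures become ranges rather than single values.
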